#### **4.5 Removal of Patients from Protocol Therapy**

Patients can be taken off the study treatment and/or study at any time at their own request, or they may be withdrawn at the discretion of the investigator for safety, behavioral or administrative reasons. The reason(s) for discontinuation of treatment will be documented and may include:

- Patient withdraws consent
- Patient is unable to comply with protocol requirements
- Patient experiences toxicity that makes continuation in the protocol unsafe
- Treating physician determines continuation on the study would not be in the patient's best interest

Notify the Principal Investigator and document the reason for study removal and the date the patient was removed from treatment in the Case Report Form. The patient should be followed-up with per protocol.

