#### **4.7 Patient Replacement**

Patients may be removed from the study at any time either via patient preference or failing to undergo either TMA or RP. If a patient is removed from the study, an additional patient may be enrolled. Patients who complete all procedures outlined in this protocol will be considered "fully evaluable", whereas those who fail to undergo any of the procedures (i.e. TMA or RP) will be considered "not fully evaluable". We will report the numbers and percent of men considered "not evaluable". If there are more than 1 or 2, we will try to figure out if there are any salient characteristics that distinguish "fully evaluable" from "not fully evaluable" patients.

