## **7.7 Monitoring Rules for Safety**

All other adverse events- such as those that are expected or are unlikely or definitely not related to the study participation- are to be reported as part of regular data submission.

---

We will pause study enrollment after 10 patients if 2 or more patients do not progress to RP and perform a thorough assessment as to ongoing safety of the study.

If a severe adverse event related to TMA occurs during TMA procedure or by follow-up phase (Day 10 ± 5) for immediate resection phase or by follow-up phase 3 (Day 40 ± 5) for delayed resection phase, we assess, discuss, and tabulate the severe adverse event.

To ensure safety, the next patient's TMA will be scheduled at least after follow-up phase of the previous patient for immediate resection phase. For delayed resection phase, the next patients for the different TMA template will be scheduled at least after follow-up phase 3 of the previous patients.

In addition, for the delayed resection phase, in the case that two in two patient who underwent the same TMA template experienced severe adverse events related to TMA, we stop to proceed the next TMA template.

We set 30% as clinically acceptable severe adverse events (defined as CDC ≥3) rate (i.e. less than 4 in 10 delayed resection cases).

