## **10.0 STATISTICAL CONSIDERATIONS**

All patients who sign the consent and are registered will be accounted for. However only those patients who undergo TMA and who undergo the radical prostatectomy will be included in the primary analyses; these will be the fully evaluable patients. Those who fail to complete the protocol as planned will be summarized; reasons for failure to complete will be examined.

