## 10.7 Data Analyses Plans

All patients who sign the consent form will be registered and entered the database. For each patient, we will list whether he received the assigned protocol (and if not, the reasons), the outcome of the procedures, compliance with the protocol (and reasons for failure to comply), adverse events with any of the procedures, MRI results, and targeted biopsy results.

- The data from the immediate resection phase and delayed resection phase will be separately evaluated. The observed ablated area in immediate resected prostatectomy specimen based on TTC staining will be compared with the predicted ablation area according to the template. The tissue viability will be evaluated by HE staining on delayed resection prostatectomy specimen.
- The comparison of the difference between the treatment effect dimensions measured histologically on the prostatectomy specimen resected after TMA and the predictive ablation charts provided by the manufacturer will be performed. For this analysis, the data from immediate resection phase and delayed resection phase are separately evaluated.
- The comparison between the treatment effect dimensions measured histologically on the prostatectomy specimen resected one month after TMA, compared to post TMA dimensions measured on the pre-RP mpMRI.
- To evaluate the intra/post-operative safety of TMA, we defined 30% as clinically acceptable severe adverse events (defined as CDC  $\geq 3$ ) rate. If the severe adverse events occur less than 30% (equivalent to less than 4 cases in 10 cases) for the delayed ablation phase, the feasibility of TMA is proved.

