### Delayed resection phase

If a severe adverse event related to TMA occurs during TMA procedure or by follow-up phase 3 (Day  $40 \pm 5$ ), we assess, discuss, and tabulate the severe adverse event. In the case that two in two patient who underwent the same TMA template experienced severe adverse events related to TMA, we stop to proceed the next TMA template. For this evaluation, TMA-related adverse events include rectal injury, urethral injury, acute urinary retention, and uncontrollable hematuria.

Adverse events are also recorded in accordance with Common Terminology Criteria for Adverse Events (CTCAE) v5.0.

- TMA procedure duration: probe-in / probe-out time, ablation time will be recorded.
- The ablation location in the prostate as seen in the KOELIS 3D map and the ablation location observed histologically on the prostatectomy specimen will be recorded.

---

- The change in functional outcomes between baseline and each follow-up visit, using IPSS, IIEF-5, EPIC-26 and uroflowmetry is recorded. For delayed resection phase, functional outcomes between baseline and follow-up phase 2 will be estimated as average change.
- The post-TMA MRI and prostate biopsy performed just prior to the delayed radical prostatectomy will be reported.

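### The delayed-phase severe-event rule treats two limits as equal that disagree at exactly 3 of 10, and does not define which men make up the 10

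*Combined protocol and SAP*

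**What the plan says.** Section 10.7 of the combined protocol and SAP sets a 30% rate of severe events (Clavien-Dindo grade 3 or higher) as acceptable. It then concludes that, if such events occur "less than 30% (equivalent to less than 4 cases in 10 cases) for the delayed ablation phase, the feasibility of TMA is proved". Section 7.7 gives the rule again: "We set 30% as clinically acceptable severe adverse events", glossed as "less than 4 in 10 delayed resection cases".

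Neither section says who belongs to the 10. The surrounding provisions are:

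- Section 10.0 defines the one analysis set in the plan: "only those patients who undergo TMA and who undergo the radical prostatectomy will be included in the primary analyses". Section 2.5 lists safety as a secondary endpoint.
- Section 4.5 allows removal when "Patient experiences toxicity that makes continuation in the protocol unsafe", and asks that removed men still be followed per protocol.
- Section 4.7 covers men who fail to undergo TMA or radical prostatectomy (RP): "If a patient is removed from the study, an additional patient may be enrolled".
- Section 7.7 adds a check: "We will pause study enrollment after 10 patients if 2 or more patients do not progress to RP".
- The delayed-phase part of Section 10.7 stops escalation if "two in two patient who underwent the same TMA template experienced severe adverse events related to TMA, we stop to proceed the next TMA template".
- Section 10.6 leaves open an extension of the sample size.

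**The concern.** This is the only numerical criterion in the plan for declaring TMA feasible; Section 10.3 sets none for the primary objective. A rule that ends in a claim of proof should give one answer for one data set. Here it may not, for two reasons.

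First, the percentage and the count are called equivalent but part company at 3 events in 10 men. Two analysts who both follow the text could report opposite conclusions.

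Second, a man who has a severe event after TMA and never reaches RP may or may not be in the rate. The only defined set would leave him out, but it is stated for other analyses, and he may be replaced. If the choice is made after the delayed-phase results are known, it can be made in the light of the verdict.

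**Working it through.** **Inputs.** Planned delayed-phase size 10 (Section 4.4.1). Limits from Sections 7.7 and 10.7. Replacement from Section 4.7. The true rates below are illustrative.

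**1. The plan's equivalence.** For x events in 10 men:

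- x/10 strictly below 0.30 holds for x = 0, 1, 2.
- x fewer than 4 holds for x = 0, 1, 2, 3.

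The stated equivalence is not reproduced. At 3/10 = 30.0% the first limit fails and the second passes; this is the only disagreement at n = 10. Reading the percentage as 30% or less does reproduce the count.

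**2. How much the choice matters.** X is binomial with n = 10 and P(X = k) = C(10,k) p^k (1−p)^(10−k). At p = 0.30:

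- P(X ≤ 2) = 0.0282 + 0.1211 + 0.2335 = 0.383
- P(X = 3) = 120 × 0.027 × 0.0824 = 0.267
- P(X ≤ 3) = 0.383 + 0.267 = 0.650

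| Assumed true rate | Pass, strictly below 30% | Pass, fewer than 4 of 10 | Exactly 3/10 |
|---|---|---|---|
| 5% | 99% | 99.9% | 1% |
| 13% | 87% | 97% | 10% |
| 20% | 68% | 88% | 20% |
| 30% | 38% | 65% | 27% |
| 40% | 17% | 38% | 21% |

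**3. One harmed man who misses RP and is replaced.** Let x be the events among the 10 men who reach RP. Counting only them gives x/10; counting everyone in whom TMA was started gives (x+1)/11.

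| x | Men reaching RP | All TMA-started | Limit strictly below 30% | Limit 30% or less |
|---|---|---|---|---|
| 2 | 2/10 = 20% | 3/11 = 27% | passes both ways | passes both ways |
| 3 | 3/10 = 30% | 4/11 = 36% | fails both ways | passes, then fails |

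One such man therefore changes the verdict only if the limit is 30% or less and the men reaching RP have exactly 3 events. Under the strict limit it takes two: 2/10 becomes 4/12 = 33%.

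**4. A number other than 10.** Three events are fewer than 4 but give 3/9 = 33% or 3/8 = 38%. A limit written as cases in 10 does not say what to do if escalation stops early or the phase is extended.

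**5. Which events count.** The 30% sentence in Section 10.7 is not restricted to TMA-related events. The delayed-phase text below it speaks of TMA-related events and lists four types.

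**6. Visit windows (a separate matter).** Section 5.3.8 puts RP at 30 ± 15 days after TMA, that is Days 15 to 45. Section 5.4.5 puts follow-up phase 3 at 10 ± 5 days after RP, so Days 20 to 60. The calendar in Section 5.5, and Sections 7.7 and 10.7, use Day 40 ± 5, that is Days 35 to 45.

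**The case against.** The strongest reply on the limit is that it is a wording slip. Sections 7.7 and 10.7 each call 30% acceptable and each give fewer than 4 in 10; all of this fits a limit of 30% or less, and only the strict wording in Section 10.7 does not. The text does lean that way. But the strict wording stands in the sentence that carries the conclusion, so the documents do not settle it.

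On size, severe events may be rare. Section 7.1.2 reports adverse events of any kind in about 13% of a HIFU series, with no additional intervention for complications, and expects fewer side effects here. Grade III in Section 7.3.2 means an intervention. HIFU is not TMA and 13% is not a severe-event rate, so this limits the concern without removing it.

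Four stronger readings are tempting, and the documents do not support them:

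- *That the rule has no denominator.* Both sections give 10 delayed-phase cases; what is missing is who they are.
- *That harmed men are excluded from the safety rate.* The restriction to men with both procedures is stated for primary analyses only. Section 10.7 lists every consenting man and his adverse events, and Section 4.5 keeps removed men in follow-up. The text permits a completers-only rate but does not require one.
- *That any replaced man flips the verdict.* Step 3 shows that one harmed man does so in one configuration only.
- *That nothing separates TMA events from RP events.* Section 7.3.4 gives the Principal Investigator a relatedness judgement for serious events, and the delayed-phase text of Section 10.7 lists TMA-related events. The 30% sentence simply does not refer to them.

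The enrollment pause and the template stop are real safeguards for patients, but neither defines the rate.

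**Conclusion.** The concern holds in two parts. The equivalence is wrong as written: the two limits give opposite verdicts at exactly 3/10. If the true rate were 30%, the pass probability would be 38% under one and 65% under the other. The chance of landing on 3/10 is 20% to 27% at true rates of 20% to 40%, about 10% at 13% and about 1% at 5%. These rates are assumptions, and the binomial model takes men as independent with the same rate on every template.

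The men behind the 10 are also undefined. The consequence is narrower: with one harmed and replaced man, the verdict turns only from 3/10 to 4/11, and only under a limit of 30% or less.

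Whether the rule counts all severe events or only TMA-related ones is a smaller gap. The Day 40 cut-off agrees with the study calendar; its conflict with Sections 5.3.8 and 5.4.5 is a separate visit-window inconsistency.

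**What to change.** In Sections 7.7 and 10.7:

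- **Limit.** Make the percentage and the count give the same verdict at 3/10, with the sponsor stating which was meant.
- **Denominator.** Define it as every delayed-phase man in whom TMA is started, whether or not RP follows. Add replacements; do not substitute them. Apply the limit as a rate if the number is not 10.
- **Numerator.** State whether the 30% rule counts only TMA-related events, as the delayed-phase text of Section 10.7 does.

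Separately, reconcile the RP and phase 3 windows in Sections 5.3.8 and 5.4.5 with Sections 5.5, 7.7 and 10.7.

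The cost is protocol wording; the data are already to be collected under Sections 5.5 and 10.7. The downside is that the denominator may exceed 10 and the observed rate may look slightly less favourable. The wording should be settled before delayed-phase results are known.

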## 1.6 Study Overview

We propose to conduct a comprehensive single institution ‘ablate and resect’ trial on Targeted Microwave Ablation (TMA) in patients undergoing robotic RP. Briefly, we will recruit patients with localized Pca undergoing RP as their treatment of choice. Immediately or 1 mo before performing RP, we will ablate the prostate with focal TMA. TMA treatment parameters will be chosen according to the manufacturer data and will be visualized in 3D using an MRI/US image-fusion platform (KOELIS Trinity®). After the prostatectomy we will study the entire prostate so that we can determine the rate of TMA-induced cell death. We will use a histologic step-sectioning approach to process the prostate that will allow us to correlate 1:1 the histology with imaging. The results of our study will provide answers to the following important questions.

**Important question #1:** Is TMA effective in eradicating all prostatic tissue and prostate cancer cells within the ablated area?

**Important question #2:** Can TMA be safely and precisely delivered to an index lesion of the prostate using the KOELIS Trinity® platform?

**Important question #3:** Do TMA predictive treated areas dimensions correlate with ablated area as determined by histological changes measured via TTC staining post-TMA on the prostatectomy specimen?

**Important question #4:** What are the best TMA parameters to achieve maximum cell kill without causing collateral complications?

**Important question #5:** How accurately post TMA MRI predict the treated area’s dimensions correlate with ablated area as determined by histological changes.

**Important question #6:** What are the MRI findings after TMA and how the MRI correlates to histology on prostate biopsy and RP specimen?

**Important question #7:** What is the perioperative AE after TMA?

**Important question #8:** What is the feasibility and safety of RP after TMA in case of ablation failure?

A total of 15 patients will be enrolled who will be identified from patients who have elected to undergo RP as their definitive treatment for PCa.

Immediately prior to RP surgery, 5 patients will undergo TMA with one ablation in the prostate index lesion.

One month prior to RP surgery, following 10 patients will undergo TMA with one ablation in the prostate index lesion.

The number of patients included may be extended considering the need to evaluate different treatment parameters (still according to manufacturer dat).

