#### **10.2 Justification of Trial Design.**

- The decision to evaluate at 5 patients in immediate resection phase would provide intraoperative safety and feasibility, and evaluation of the ablated area on the radical prostatectomy specimen assessed by TCC stanning according to TMA delivery protocols. The decision to evaluate at 10 patients in delayed resection phase would provide intraoperative safety and feasibility, in addition to estimate of the short-term safety after TMA, evaluation for functional status (urinary symptoms, potency, incontinence), PSA response, MRI evaluation, prostate biopsy evaluation, safety and feasibility of salvage prostatectomy after TMA, and evaluate tissue viability on HE stanning. Additionally, The post-TMA MRI and prostate biopsy performed just prior to the delayed radical prostatectomy will be used to predict/evaluate the actual prostatectomy findings.

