### Immediate resection phase

If a severe adverse event related to TMA occurs during TMA procedure or by follow-up phase (Day  $10 \pm 5$ ), we assess, discuss, and tabulate the severe adverse event. For this evaluation, TMA-related adverse events include rectal injury, and urethral injury.

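### The rule that declares TMA feasibility proved is scored on the 10 delayed-resection men only, so severe procedural injuries in the five immediate-resection men have no formal bearing on that conclusion

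*Combined protocol and SAP*

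**What the plan says.** Section 10.7 gives the purpose of the limit without restriction by phase: "To evaluate the intra/post-operative safety of TMA, we defined 30% as clinically acceptable severe adverse events". The same bullet then applies it to 10 men: if severe events stay under 30%, equated there with fewer than 4 of 10, then "for the delayed ablation phase, the feasibility of TMA is proved". Section 7.7 states the limit again with the same denominator: "i.e. less than 4 in 10 delayed resection cases".

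For the first five men, the immediate-resection part of Section 10.7 says that if a severe TMA-related event occurs, "we assess, discuss, and tabulate the severe adverse event". The events listed are rectal and urethral injury, up to the Day 10 visit. No threshold follows. The delayed-resection part lists those two injuries plus acute urinary retention and uncontrollable hematuria, up to about Day 40.

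Section 10.2 gives the first phase a safety role: "The decision to evaluate at 5 patients in immediate resection phase would provide intraoperative safety and feasibility". Section 5.3.7 says that preparation, positioning, planning and delivery of TMA in the later men are as in the first five, and Section 4.2 uses the same five templates in both phases.

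**The concern.** The stated purpose covers intra-operative safety of TMA, and the conclusion is about TMA in general. The evidence admitted is two thirds of the procedures. A rectal or urethral injury caused by the antenna is the same kind of event in either phase, both phases list it, and Section 10.7 already asks whether such an event in the first five men is TMA-related. Section 4.2 says that no standard TMA dosage exists for this setting, and each template is first used in those five men.

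This is the only rule in the plan that leads to a declaration of feasibility. Section 10.3 also addresses feasibility, through viable tissue on histology, but sets no threshold. Section 1.3 says that success could lead to a multicenter study. What is at stake is therefore a published statement that feasibility is proved, made by a rule that cannot respond to procedural injuries in a third of the men treated.

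**Working it through.** **Inputs.** Total men: "A total of 15 patients will be enrolled" (Section 1.6). Immediate phase: 5 men; delayed phase: 10 men (Section 1.6). Limit: 30%, equated with fewer than 4 of 10 (Sections 10.7 and 7.7). The plan gives no alpha, power or expected event rate, and Section 10.6 says that 15 is a practical number.

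**The plan's own figure.** Strictly under 30% of 10 allows at most 2 events, because 3/10 is exactly 30%. Fewer than 4 allows 3. The stated count matches only if the limit is read as 30% or less. Both readings are carried below. The point does not depend on which is meant.

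**Share outside the rule.** 5/15 = 33.3% of TMA procedures.

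**Range of overall results that give the same verdict.**
- 3/10 delayed, 0/5 immediate: 3/15 = 20.0%. Passes.
- 3/10 delayed, 2/5 immediate: 5/15 = 33.3%. Passes, although all men together exceed 30%.
- 3/10 delayed, 5/5 immediate: 8/15 = 53.3%. Passes.
- Strict reading, 2/10 delayed, 5/5 immediate: 7/15 = 46.7%. Passes.

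**How often the conflict arises.** Assume independent men, one common true risk of 30%, and the same event definition in both phases. Let A be the events in 10 delayed men and B those in 5 immediate men. The limit over 15 men is 0.30 × 15 = 4.5, so 5 or more events exceed it. The conflict is A ≤ 3 with A + B ≥ 5.

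| A | P(A) | B needed | P(B) | Product |
|---|---|---|---|---|
| 0 | 0.0282 | 5 | 0.0024 | 0.0001 |
| 1 | 0.1211 | 4 or more | 0.0308 | 0.0037 |
| 2 | 0.2335 | 3 or more | 0.1631 | 0.0381 |
| 3 | 0.2668 | 2 or more | 0.4718 | 0.1259 |

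The sum is 0.1678, or 16.8%. Without the last row (at most 2 of 10) it is 0.0419, or 4.2%. For comparison, the delayed-only rule passes with probability 0.650 at this risk (0.383 on the strict reading).

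Other assumed true risks give these conflict probabilities: at 20%, 7.2% (1.9% strict); at 40%, 18.5% (4.2% strict).

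**What plain pooling would do.** With 4/10 delayed and 0/5 immediate events, the present rule fails. Pooled, 4/15 = 26.7% would pass. Replacing the denominator of 10 by 15 can therefore turn a failure into a pass.

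**The case against.** The strongest reply is that the scope is a design choice. Section 1.3 uses the first five cases to work out the TMA protocol and the following ten for practical feasibility. Section 10.6 assigns template ablation areas to the first phase and short-term safety and feasibility to the second. Section 10.7 says that data from the two phases are evaluated separately, and Section 10.2 credits the delayed phase with intraoperative safety too. Event lists and windows differ, and in the first five men prostatectomy follows under the same anesthesia, which blurs attribution. All of this stands as a reason not to pool the two phases. It does not explain why a rectal or urethral injury judged TMA-related in the first five men should have no weight in a general conclusion about intra-operative safety.

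Safeguards also exist: spacing between patients and case review (Section 7.7), physician modification (Section 4.2) and committee oversight (Section 11.7.3). They govern conduct and do not feed the feasibility conclusion.

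A reader might infer more than the documents support:
- *That the rate behind the conclusion is biased downward.* This is not shown. With equal risk in both phases, the delayed-only estimate is unbiased for that risk, and the shorter list and window in the first phase could make a pooled rate lower.
- *That this is the only decision rule, or that the five men are ignored.* Section 7.7 also has a same-template rule and an enrollment pause after 10 patients, and that count includes the first five. Section 10.7 lists adverse events for every man, and the safety endpoint in Section 2.5 has no phase limit.
- *That the verdict is very likely to be wrong.* At a true 30% risk, the chance of at least one event among five men is 1 − 0.7^5 = 83.2%, but one event need not conflict with the verdict. The relevant figures are 16.8% and 4.2%.

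**Conclusion.** The point holds for the rule as written. The only route to a declaration of feasibility is scored on 10 of 15 men, so severe TMA-related injuries in the other five cannot alter it. That does not fit the rule's stated purpose or the role that Section 10.2 gives the first phase.

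The same verdict is compatible with overall rates from 20% to 53% when 3 of 10 delayed men have events. The 53% case is a logical extreme, and 2 of 5 immediate events already take the overall rate above 30%. The 16.8% (4.2% strict) rests on independent men, a true 30% risk in every man and one event definition in both phases. The two event lists differ, so it shows the scale of the conflict and does not predict it. The share of one third would change if enrollment is extended, as Section 10.6 allows.

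The separate evaluation of the phases is not itself an error. The defect is a general conclusion drawn from a delayed-phase criterion.

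**What to change.** In Section 10.7, and in matching words in Section 7.7:

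1. Keep the present criterion on the delayed-resection men and name it a delayed-phase safety criterion.
2. Before any general statement that TMA feasibility is shown, also require that severe (Clavien-Dindo grade 3 or higher) TMA-related injuries on both phases' lists, rectal and urethral injury, be judged over all men who had TMA against the percentage the plan already states. With 15 men, at most 4 would meet it whether the limit is read as under 30% or as 30% or less (4/15 = 26.7%; 5/15 = 33.3%).
3. Report immediate-only and delayed-only counts beside it. This matters because 4 of 5 immediate and 0 of 10 delayed injuries would still meet the all-men check.
4. If the second requirement is not adopted, limit the conclusion to the delayed phase.

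Because both requirements must be met, the existing criterion cannot be diluted. The change is about a sentence in each section, uses data already collected, and leaves treatment, escalation and stopping rules as they are. It should be made before the data are analysed, since adding these men later would be post hoc. The costs are that relatedness is less certain in the immediate-resection men, because prostatectomy follows under the same anesthesia, and that the general conclusion becomes slightly harder to reach.

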## **2.1 Primary Objectives**

To determine the feasibility of transperineal targeted microwave ablation of an MRI-identified index prostate cancer in patients undergoing radical prostatectomy.

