## **2.4 Primary Endpoints**

The ablated area on the radical prostatectomy specimen assessed by viability tissue staining (TTC).

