## 5.5

## Study Calendar

First 5 patients

	Screening visit	Treatment date			Follow-up Phase	Completion phase
		Day 0			Day 10 ( $\pm 5$ )	Day 30 day ( $\pm 10$ )
		OR pre-TMA	TMA	OR post-TMA		
Medical history	X					
Demographics	X					
Medication review	X					
Adverse Event assessment	X	X		X	X	X
Physical Exam	X				X	X
Vital Signs (temperature, pulse, respiration, BP, (height and weight -only on screening)	X				X	X
Hematology, full blood count, renal function and coags	X					
PSA measurement	X					X
Patient eligibility review, enrollment	X					
Informed Consent	X					
MRI	X					
Uroflowmetry	X					X
Catheter removal					X	
IPSS, IIEF-5 and EPIC-26 questionnaires	X					X
Urine analysis and culture	X					
Radical prostatectomy				X		
TMA delivery			X			
Pathology				X 		

1: Pathologic evaluation including TTC staining is performed immediately after RP.

Following 10 patients

	Screening visit	Treatment date			Follow-up Phase1	Follow-up Phase2	RP date	Follow-up Phase3	Completion phase
		Day 0			Day 10 (±5)	Day 30 (±5) 	Day 30 (±5)	Day 40 (±5)	60 days (±10 days)
		OR pre-TMA	T M A	OR post-TMA					
Medical history	X								
Demographics	X								
Medication review	X								
Adverse Event assessment	X	X		X	X	X	X	X	X
Physical Exam	X				X	X		X	X
Vital Signs (temperature, pulse, respiration, BP, (height and weight -only on screening)		X			X			X	X
Hematology, full blood count, renal function and coags	X								
PSA measurement	X					X			X
Patient eligibility review, enrollment	X								
Informed Consent	X								
MRI	X					X			
Uroflowmetry	X					X			X
Catheter removal					X			X	
IPSS, IIEF-5 and EPIC-26 questionnaires	X					X			X
Urine analysis and culture	X								
Intra-operative prostate biopsy							X		
Radical prostatectomy							X		
TMA delivery			X						
Pathology							X 		

---

- 2: The date of Follow-up Phase2 is scheduled 1-5 days before RP date.
- 3: Pathologic evaluation without TTC staining is performed after RP.

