## **6.0 MEASUREMENT OF EFFECT**

The main effect we will measure to achieve our primary objective is the treatment effect (proportion of dead tissue - benign and cancerous) inside the TMA-treated zone on the prostatectomy specimen. The excised prostate will be sliced at 4 mm intervals. Each slice will be embedded, and a pathologist will examine slides corresponding to each slice. The pathologist will be blinded to MR and TRUS imaging results. TTC and/or H&E staining are performed to determine thermal ablation zone size/location/relationship to urethra seminal vesicles capsule and other structures.

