#### **10.3 Primary Objective Statistical Considerations**

To determine the feasibility of transperineal targeted microwave ablation of an MRI-identified index prostate tumor in patients undergoing radical prostatectomy, we will evaluate the viable tissue remaining after TMA using histologic examination of excised prostate specimen.

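### Section 10.7 concludes on feasibility, the primary objective, from severe adverse events alone, so no specimen result can change the stated conclusion

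*Combined protocol and SAP*

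**What the plan says.** Section 2.1 states the primary objective: "To determine the feasibility of transperineal targeted microwave ablation of an MRI-identified index prostate cancer in patients undergoing radical prostatectomy". It names feasibility without defining it. Other sections supply the content:

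- Section 1.4 says feasibility will be assessed through efficacy on prostatectomy histology, precision of guidance, and safety.
- Section 2.4 gives the primary endpoint as "The ablated area on the radical prostatectomy specimen assessed by viability tissue staining (TTC").
- Section 6.0 says "The main effect we will measure to achieve our primary objective is the treatment effect", defined there as the proportion of dead tissue inside the treated zone, read on TTC and/or H&E.
- Section 10.3 says that, to determine feasibility, "we will evaluate the viable tissue remaining after TMA using histologic examination of excised prostate specimen".

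Section 10.7 analyses the immediate and delayed phases separately. In the immediate phase the observed area "based on TTC staining will be compared with the predicted ablation area according to the template"; in the delayed phase viability is assessed on H&E. Neither step leads to a stated conclusion. A later bullet in the same section, introduced as an evaluation of safety, does conclude. Its condition is the 30% limit on severe events, which it equates with fewer than 4 of 10 men, and the consequence it draws is this: "for the delayed ablation phase, the feasibility of TMA is proved".

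The rule is read in the 10 delayed-resection men. For them the Study Calendar notes: "Pathologic evaluation without TTC staining is performed after RP".

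**The concern.** The objective, endpoint and effect measure all point to tissue destruction on the specimen, while the one conclusion points to adverse events. A safety result is therefore labelled feasibility. If the rule were applied as written, TMA that left the target largely viable but caused few severe events would be reported as feasible.

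This matters because Section 10.1 presents the study as a test of whether TMA is promising as a stand-alone treatment that could replace prostatectomy or radiation, and Section 1.3 foresees a multicenter study if it succeeds. A statement that feasibility was proved would carry weight in that decision without having drawn on the primary endpoint.

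**Working it through.** **Is there another feasibility rule?** The candidates are:

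| Place | Input | What follows |
|---|---|---|
| 10.3 | Viable tissue on histology | Evaluated; no conclusion stated |
| 10.7, TTC and H&E bullet | Observed against predicted area; viability | Compared and evaluated; no conclusion stated |
| 7.7, 30% limit | Severe events | Called clinically acceptable; no feasibility conclusion |
| 7.7, pause rule | Men not reaching prostatectomy | Pause and safety assessment |
| 7.7 and 10.7, template rule | Severe events in two of two men | No progression to the next template |
| 10.8, response | None | Not applicable |
| 10.7, safety bullet | Severe events in the delayed phase | Feasibility declared proved |

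Only the last row concludes on feasibility.

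**The plan's own cut-off.** A rate strictly below 30% of 10 men allows 0, 1 or 2 events (2/10 = 20%; 3/10 = 30% is not below 30%). Fewer than 4 cases allows 0 to 3. The two statements disagree at exactly 3 events. That is a separate inconsistency to be reconciled, so both readings are shown.

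**Chance of declaring feasibility.** Let p be the true severe-event rate and c the largest number of events allowed (2 or 3). Then

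P(declare feasible) = Σ (x = 0 to c) C(10, x) p^x (1 − p)^(10 − x).

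No term for ablated or viable tissue appears. At p = 0.10:

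- x = 0: 0.9^10 = 0.3487
- x = 1: 10 × 0.1 × 0.9^9 = 0.3874
- x = 2: 45 × 0.01 × 0.9^8 = 0.1937
- x = 3: 120 × 0.001 × 0.9^7 = 0.0574

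The first three terms sum to 0.930 and all four to 0.987.

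The protocol gives no planning value for the severe-event rate, so the rates below are assumptions.

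| Severe-event rate p | At most 2 events | At most 3 events |
|---|---|---|
| 5% | 0.988 | 0.999 |
| 10% | 0.930 | 0.987 |
| 20% | 0.678 | 0.879 |
| 30% | 0.383 | 0.650 |

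**Contrast of extremes.** Suppose the specimens show fully viable tissue in all 5 immediate and all 10 delayed men, or fully non-viable treated zones in all 15. For a given p, the table is the same in both cases.

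**The case against.** The strongest reply is that this is a mislabel, not a designed primary decision rule. The sentence closes a safety bullet, Section 7.7 states the same limit with no feasibility claim, and Section 10.3 never mentions adverse events. Safety is also a legitimate component of feasibility under Section 1.4, and Section 10.6 assigns short-term safety and feasibility to the delayed phase. In a small exploratory study sized by cost, descriptive reporting of histology is defensible. All of this stands. It argues for a short repair, but does not rescue the sentence: the plan makes a declaration on its primary objective and bases it on safety alone.

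A reader might infer more than the documents support:

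- **That the primary endpoint has no role at all.** Section 10.3 evaluates viable tissue for the primary objective, Section 10.7 compares TTC area with prediction, and Section 4.2 links escalation to the histologically ablated area. Histology lacks a role only in the stated conclusion.
- **That the delayed men contribute nothing to the primary objective.** This is true only of the TTC endpoint as worded in Section 2.4. Section 6.0 admits H&E and Section 10.3 refers to histologic examination generally.
- **That the rule rewards under-treatment.** It is plausible that less ablation causes fewer severe events, but no figure in the documents shows it.
- **That a pooled pass mark across men is required.** In Section 4.2 the five immediate men receive five different templates, and the ten delayed men receive two per template. A pooled success count would mix deliberately small ablations with the largest, and statisticians could reasonably differ on whether any numeric limit is needed.

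**Conclusion.** The point holds. As written, Section 10.7 declares the primary objective met from a secondary safety endpoint, and no specimen result can change that declaration. Over assumed severe-event rates of 5% to 30%, the probability of declaring feasibility runs from 0.988 down to 0.383 with at most 2 events, and from 0.999 down to 0.650 with at most 3, regardless of what was ablated.

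These figures assume independent men, one common severe-event rate across templates, and all 10 delayed men treated, with no early halt under the template rule. The main finding needs none of these assumptions, because it follows from the wording: ablation is not an input to the rule.

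The fault is the use of safety alone. It does not follow that safety is irrelevant to feasibility, or that the histologic work is missing from the plan.

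**What to change.** 1. In Section 10.7, call the 30% rule the short-term safety criterion and delete its closing clause, which says that feasibility is proved.
2. In Sections 10.3 and 10.7, state that the feasibility conclusion rests on three elements together: the specimen results, delivery of the planned TMA, and the safety criterion. Add that meeting the safety criterion alone does not establish feasibility.
3. Specify the specimen results: TTC in the immediate phase and H&E in the delayed phase, reported for each template as the proportion of non-viable tissue in the treated zone and as observed against predicted dimensions.
4. If the sponsor wants a numeric histologic limit, set it in advance and by template, not pooled over the five templates. The plan gives one TTC specimen and two H&E specimens per template.

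The cost is about a paragraph of text across the two sections. The feasibility claim becomes harder to reach. No additional patients, procedures or data are needed.
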